5.2.1.2. Supply, Packaging, and Labeling

Study drug will be supplied as 5 mL of aqueous solution in 10 mL glass vials with 10 mg/mL of INCAGN01949. Study drug will be packaged as open-labeled supplies, and each vial will be labeled and placed in a carton. The Pharmacy Manual contains additional information regarding supply, packaging, and labeling of study drug.

The investigator shall take responsibility for and shall take all steps to maintain appropriate records and ensure appropriate supply, storage, handling, distribution, and usage of study drug in accordance with the Protocol and any applicable laws and regulations.

All Incyte investigational product labels will be in the local language and will comply with the legal requirements of each country.

5.2.1.3. INCAGN01949 Storage

Study drug must be stored refrigerated (2°C-8°C) and protected from light, in a secure, limited access location. Receipt and dispensing of study drug must be recorded by an authorized person at the study site. Study drug may not be used for any purpose other than that stated in the Protocol. The Pharmacy Manual contains additional information regarding storage of study drug.

5.2.2. Standard Immune Therapies

5.2.2.1. Nivolumab

Nivolumab will be administered IV per instructions in the package insert at the site, at a dose that is dependent on the assigned treatment group as follows:

- Doublet Treatment Groups A and F: 240 mg on Day 1 of every 2-week (ie, 14-day) cycle.
- Doublet Treatment Groups C, G, and H: 240 mg on Day 1 of every 2-week (ie, 14-day) cycle beginning on Cycle 3 Day 1.
- Triplet Treatment Groups D and J: 3 mg/kg on Day 1 of every 2-week (ie, 14-day) cycle.
- Triplet Treatment Groups E, K, and L: 3 mg/kg on Day of every 2-week (ie, 14-day) cycle beginning on Cycle 3 Day 1.

Alternate dose administration schedules may also be explored depending on [REDACTED]
[REDACTED] safety results.

Nivolumab will be administered at least 30 minutes after the end of the infusion of INCAGN01949 (when applicable), and subjects will continue to receive nivolumab for up to 24 months as long as the subject is considered to derive ongoing clinical benefit at the discretion of the investigator, and the subject has not met any of the Protocol-defined conditions for treatment withdrawal.

Nivolumab is commercially available. Investigators are responsible for ensuring that subjects receive commercially available supplies of nivolumab for the entire duration of study participation. Incyte may provide certain standard-of-care medications such as nivolumab where required by applicable law or specific regulation or under other circumstances when subjects may not otherwise have access to them. Nivolumab must be used in accordance with the storage conditions and shelf life in the manufacturer's approved label.

5.2.2.2. Ipilimumab

Ipilimumab will be administered IV per instructions provided in the package insert at the site, at a dose that is dependent on the assigned treatment group as follows:

- Doublet Treatment Group B and Triplet Treatment Group D: 1 mg/kg administered every 6 weeks (eg, 42 days) beginning on Cycle 1 Day 1.
- Triplet Treatment Group J: 1 mg/kg administered every 6 weeks (eg, 42 days) beginning on Cycle 1 Day 1.
- Triplet Treatment Groups E, K, and L: 1 mg/kg administered every 6 weeks (eg, 42 days) beginning on Cycle 3 Day 1.

Alternate dose administration schedules may also be explored depending on [REDACTED]
[REDACTED] safety results.

Ipilimumab will be administered at least 30 minutes after the end of the infusion of INCAGN01949 (when administered on the same day). Ipilimumab will always be administered after INCAGN01949 and nivolumab. Subjects will continue to receive ipilimumab for up to 24 months as long as the subject is considered to derive ongoing clinical benefit at the discretion of the investigator, and the subject has not met any of the Protocol-defined conditions for treatment withdrawal.

At the sponsor's discretion, once the MTD or PAD of INCAGN01949 has been established with ipilimumab at 1 mg/kg Q6W, a higher dose of ipilimumab at 3 mg/kg Q6W and/or 3 mg/kg Q3W for 4 doses may be tested.

Ipilimumab is commercially available. Investigators are responsible for ensuring that subjects receive commercially available supplies of ipilimumab for the entire duration of study participation. Incyte may provide certain standard-of-care medications such as ipilimumab where required by applicable law or specific regulation or under other circumstances when subjects may not otherwise have access to them. Ipilimumab must be used in accordance with the storage conditions and shelf life in the manufacturer's approved label.

5.3. Treatment Compliance

5.3.1. Treatment Compliance of INCAGN01949, Nivolumab, and Ipilimumab

INCAGN01949, nivolumab, and ipilimumab are administered as an IV infusion by site personnel. Receipt of infusions will be documented by the site staff and monitored by the sponsor/designee.

5.4. Treatment Interruptions and Adjustments

5.4.1. Dose Modifications

Selections and modifications to the study drug (INCAGN01949) are planned for dose-escalation cohorts (see Section 4.1.1). Dose interruptions of study drug may also occur for individual study subjects. The identification of DLTs will define the doses of INCAGN01949 used in planned cohorts (see Section 5.4.2). Further, the occurrence of DLTs and other toxicities (related or unrelated to study drug) will guide decisions for treatment interruptions and discontinuation for individual subjects. Dose interruptions of INCAGN01949 should not be made during the DLT observation period without discussion with the medical monitor. Intrasubject dose escalation will not be permitted.

No dose reductions of INCAGN01949, nivolumab, or ipilimumab are allowed for the management of toxicities of individual subjects. Doses of INCAGN01949, nivolumab, and ipilimumab may be delayed for toxicity management (see Section 5.4.6).

5.4.2. Dose-Limiting Toxicity and Determination of Maximum Tolerated Dose

The evaluation period for DLTs will begin on Cycle 1 Day 1 and will continue up to and including study Day 28 for subjects in Phase 1 Part 1 (Treatment Groups A, B, and D). All DLTs will be assessed by the investigator using CTCAE v4.03 criteria. A DLT will be defined as the occurrence of any toxicity in Table 8, except those that are clearly and incontrovertibly due to disease progression or extraneous causes.

Individual subject dose interruptions of study drug may be made based on events observed at any time during treatment; however, for the purposes of dose cohort escalation/de-escalation, expanding a dose cohort, and determining the MTD of INCAGN01949, decisions will be made based on events that are observed during the DLT evaluation period. A lower MTD may subsequently be determined based on relevant toxicities that become evident after the end of the DLT evaluation period.

Table 8: Definition of Dose-Limiting Toxicity

Nonhematologic toxicity	

 Any liver function abnormalities that meet the definition of Hy's law^a. Any grade encephalopathy. Any \geq Grade 3 nonhematologic toxicity EXCEPT the following: 
 Transient (\leq 72 hours) abnormal electrolyte values, is not clinically complicated, and resolves spontaneously or responds to conventional medical interventions. Nausea, vomiting, and diarrhea adequately controlled with supportive care within 48 hours. Changes in cholesterol and triglycerides. An event clearly and incontrovertibly due to disease progression or extraneous causes. Grade \geq 3 changes in amylase and lipase that is not associated with symptoms or clinical manifestations of pancreatitis. Grade 3 fatigue $<$ 1 week. Single or nonfasting elevations in blood glucose (ie, blood glucose excursions will be considered toxicities if fasting blood glucose is elevated on 2 separate occasions). Grade 3 rash in the absence of desquamation, with no mucosal involvement, that does not require systemic steroids, and that resolves to Grade 1 within 14 days. 	
Hematologic toxicity	

 Grade 3 thrombocytopenia with clinically significant bleeding (ie, requires hospitalization, transfusion of blood products, or other urgent medical intervention). Grade 4 neutropenia or thrombocytopenia lasting $>$ 7 days. Any grade febrile neutropenia (fever $>$ 101°F/38.3°C). Grade 4 anemia not explained by underlying disease or some other concomitant disorder. 	
Immune-related toxicity^b	

 \geq Grade 2 ocular irAEs will be considered a DLT. Grade 3 irAEs that do not improve to baseline or at least Grade 1 in $<$ 5 days with appropriate care or with corticosteroid therapy will be considered a DLT. Grade 4 irAEs will be considered a DLT regardless of duration. \geq Grade 2 pneumonitis 	
General	

 Any death not clearly due to the underlying disease or extraneous causes. Inability to receive the planned number of doses within the 28-day DLT period due to toxicity, regardless of grade, will be considered a DLT. 	
MTD	

 In Phase 1 Part 1 of the study, the MTD will be defined as 1 dose level below that at which \geq one-third of subjects in a particular cohort have DLTs. In Phase 2 of the study, toxicities will continue to be monitored. If the cumulative incidence of Grade 3 or Grade 4 INCAGN01949-related AEs occurs in $>$ 40% of subjects in a particular treatment group after 6 subjects have been enrolled, then further enrollment in that treatment group will be interrupted until the sponsor, investigators, and regulatory authorities (if applicable) determine the appropriate course of action (eg, lower the dose of INCAGN01949, change dose frequency, etc). If a treatment group is discontinued due to toxicity, it may be re-initiated at a previously tested lower dose level and/or alternate dosing schedule. All AEs, regardless of the time of occurrence on study, may be considered for DLT determination purposes. 	

^a Hy's law is defined as 1) ALT or AST elevation \geq 3 times ULN AND 2) total bilirubin $>$ 2 times ULN, without initial findings of cholestasis (elevated serum alkaline phosphatase), AND 3) no other apparent possible causes of aminotransferase elevation and hyperbilirubinemia, including, but not limited to, viral hepatitis, pre-existing chronic or acute liver disease, or the administration of other drug(s) known to be hepatotoxic.

^b Immune-related AEs are a diagnosis of exclusion, after alternative etiologies have been ruled out.

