2. STUDY OBJECTIVES AND ENDPOINTS

2.1. Study Objectives

2.1.1. Primary Objectives

Phase 1

- To evaluate the safety, tolerability, and DLTs of INCAGN01949 in combination with immune therapies and to define the recommended dose(s) of INCAGN01949 when given in combination with immune therapies.

[figure not shown]
Phase 2

- To evaluate the efficacy of INCAGN01949 when given in combination with immune therapies by assessing ORR per RECIST v1.1.

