4.1.2.1. Doublet Immune Therapy Combination for Safety Expansion

4.1.2.1.1. Treatment Group C (INCAGN01949 Run-In Followed by Concurrent Dosing With Nivolumab)

Treatment Group C will treat subjects with a 2-dose run-in of INCAGN01949 Q2W at the assigned dose level followed by the combination of INCAGN01949 Q2W plus nivolumab 240 mg Q2W (starting at Cycle 3, see figure in [Table 5](#)).

Table 5: Doublet Immune Therapy Treatment Group for Safety Expansion

Treatment Group C	INCAGN01949 Run-In Followed by Concurrent Dosing	Nivolumab
	See INCAGN01949 dose cohorts (Table 2) Q2W starting at Cycle 1	240 mg Q2W starting at Cycle 3

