4.3.2. Replacement of Subjects

Subjects may be replaced for any of the following reasons:

- In Phase 1, any subject who withdraws from treatment before the completion of the DLT observation period for any reason other than a DLT (ie, is not evaluable for DLTs; see Section 5.4.2), may be replaced to ensure a minimum number of evaluable subjects.
- [REDACTED]
- Subjects who do not meet the eligibility requirements of the study may be replaced.

Subjects who meet any of the criteria for replacement may remain on study for evaluation as outlined in Section 9.1 and Section 9.2.

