8.2. Adverse Events

8.2.1. Adverse Event Definitions

A TEAE is any AE either reported for the first time or worsening of a pre-existing event after first dose of study drug. For the subjects in the FAS population, analysis of AEs (as discussed below) will be limited to TEAEs, but data listings will include all AEs regardless of their timing in relation to study drug administration.

Adverse events will be tabulated by MedDRA PT and SOC. Severity of AEs will be graded using the National Cancer Institute CTCAE. The CTCAE version 4.03 is used for this study. The CTCAE reporting guidelines and grading details are available on the Cancer Therapy Evaluation Program website.

The subset of AEs considered by the investigator to be related to INCAGN01949, nivolumab, or ipilimumab will be considered to be treatment-related AEs and will be summarized. If the investigator does not specify the relationship of the AE to study drug, the AE will be considered to be treatment-related. The incidence of AEs and treatment-related AEs will be tabulated. In addition, SAEs will also be tabulated.

A grading (severity) scale is provided for each AE term. If the toxicity is not included in the CTCAE v4.03 criteria, it will be rated on a scale of 1 to 5 as follows: 1 = mild, 2 = moderate, 3 = severe, 4 = life-threatening, and 5 = death related to AE. All toxicities will be graded based on the worst level reached, not the level they may have reached if they had not been treated. When the intensity of an AE changes over time for a reporting period (eg, between visits), each

change in intensity will be collected as an AE until the event resolves. Only the worst grade will be reported in AE summaries. Also, the Grade 3 or higher AEs will be summarized.

Any missing onset date, causality, or severity must be queried for resolution. Unresolved missing causality and severity will be handled according to the following rules:

- An unresolved missing causality will be considered treatment-related.
- An unresolved missing severity will be identified as an unknown severity.

For purposes of analysis, all AEs will be considered TEAEs unless the AE can unequivocally be defined as not treatment-emergent.

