8.2.2. Dose-Limiting Toxicities

The number of subjects with DLTs and the type of DLT will be listed by dose level and treatment group. An AE for a subject will be identified as a DLT if the event is recorded as a Protocol-defined DLT on the AE CRF.

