8.2.4. Adverse Event Summaries

An overall summary of AEs by treatment group and by tumor type as applicable will include the following:

- Number (%) of subjects reporting any TEAEs
- Number (%) of subjects reporting any DLTs
- Number (%) of subjects reporting any SAEs
- Number (%) of subjects reporting any Grade 3 or higher TEAEs
- Number (%) of subjects reporting any TEAEs related to INCAGN01949
- Number (%) of subjects reporting any TEAEs related to nivolumab
- Number (%) of subjects reporting any TEAEs related to ipilimumab
- Number (%) of subjects who temporarily interrupted INCAGN01949 because of TEAEs
- Number (%) of subjects who temporarily interrupted nivolumab because of TEAEs
- Number (%) of subjects who temporarily interrupted ipilimumab because of TEAEs
- Number (%) of subjects who permanently discontinued INCAGN01949 because of TEAEs
- Number (%) of subjects with INCAGN01949 dose reductions because of TEAEs
- Number (%) of subjects who had a fatal TEAE
- Number (%) of subjects who withdrew from study because of an TEAE

The following summaries will be produced by MedDRA term:

- Summary of TEAEs by SOC and PT
- Summary of TEAEs by PT in decreasing order of frequency
- Summary of TEAEs by SOC, PT, and maximum severity
- Summary of Grade 3 or higher TEAEs by SOC and PT
- Summary of INCAGN01949 treatment-related AEs by SOC and PT
- Summary of nivolumab treatment-related AEs by SOC and PT
- Summary of ipilimumab treatment-related AEs by SOC and PT
- Summary of Grade 3 or higher INCAGN01949 treatment-related AEs by PT in descending order of frequency
- Summary of Grade 3 or higher nivolumab treatment-related AEs by PT in descending order of frequency

- Summary of Grade 3 or higher ipilimumab treatment-related AEs by PT in descending order of frequency
- Summary of treatment-emergent SAEs by SOC and PT
- Summary of treatment-emergent SAEs by PT in descending order of frequency
- Summary of treatment-emergent non-SAE by SOC and PT.
- Summary of treatment-related SAEs by SOC and PT
- Summary of TEAEs leading to INCAGN01949 dose reduction by SOC and PT
- Summary of TEAEs leading to INCAGN01949 dose interruption by SOC and PT
- Summary of TEAEs leading to nivolumab dose interruption by SOC and PT
- Summary of TEAEs leading to ipilimumab dose interruption by SOC and PT
- Summary of TEAEs leading to discontinuation of INCAGN01949 by SOC and PT
- Summary of TEAEs leading to death by SOC and PT

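### Run-in Groups C and E have no DLT evaluation period, yet the SAP prints a DLT percentage for them, and its main TEAE tables pool their run-in monotherapy with combination exposure

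*Protocol*

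**What the plan says.** **DLT period.** Under Protocol 5.4.2 the evaluation period opens on the first day of Cycle 1; it "will continue up to and including study Day 28 for subjects in Phase 1 Part 1 (Treatment Groups A, B, and D"). Escalation, cohort expansion and MTD "decisions will be made based on events that are observed during the DLT evaluation period". Protocol Tables 3 and 4 (Groups A, B and D) carry a column for the DLT observation period. Tables 5 and 6 (Groups C and E) have no such column.

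**Run-in schedule.** Group C receives two doses of INCAGN01949 alone and then adds nivolumab "240 mg Q2W (starting at Cycle 3"). Group E follows the same pattern, with nivolumab and ipilimumab both starting at Cycle 3 (Protocol 4.1.2.2.1).

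**Objective.** The Phase 1 primary objective begins "To evaluate the safety, tolerability, and DLTs of INCAGN01949 in combination with immune therapies" (Protocol 2.1.1). It does not separate Part 1 from Part 2.

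**Reporting.** SAP 5.2 lists C and E among the treatment groups. SAP 8.2.2 says "The number of subjects with DLTs and the type of DLT will be listed by dose level and treatment group", and a DLT is any event the site records as protocol-defined on the AE form. SAP 8.2.4 adds "Number (%) of subjects reporting any DLTs". Planned Table 3.2.1.1 presents the overall AE summary by treatment group and dose on the Phase 1 FAS. SAP 9.1.1 has the DMC review DLT rates in every treatment group.

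**TEAEs.** "A TEAE is any AE either reported for the first time or worsening of a pre-existing event after first dose of study drug" (SAP 8.2.1).

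**The concern.** Two things in the Phase 1 report could mislead for Groups C and E.

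The first is the DLT row. With no evaluation period, a site has no protocol basis for flagging a DLT in C or E, so the cell will probably show 0 of n. Nothing in the table tells the reader that this zero differs in kind from a zero in A or D, where a 28-day assessment stands behind it.

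The second is the TEAE tables, which a reader would turn to instead. They count from the first dose of any study drug. In C and E that includes the whole monotherapy run-in, and it includes subjects who left before any partner drug was given. The combination-period safety of the run-in schedule is therefore not visible in the all-cause or INCAGN01949-related tables.

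Enrollment stopped at 52 subjects and only Phase 1 analyses will be done (Protocol 9), so these tables are the study's output.

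**Working it through.** **1. The plan's own DLT figures.** Protocol Table 20 (repeated as SAP Table 3) gives the probability of escalation under the 3 + 3 + 3 rule. A dose is escalated after 0/3; after 1/3 then 0/3; or after 1/3, 1/3, then 0/3. With q = (1−p)³ and o = 3p(1−p)², P(escalate) = q(1 + o + o²).

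| True DLT rate | Computed | Stated |
|---|---|---|
| 20% | 78.41% | 78.4% |
| 30% | 56.10% | 56.1% |
| 40% | 34.96% | 35.0% |
| 50% | 18.95% | 18.9% |
| 60% | 8.77% | 8.8% |

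The figures reproduce. They describe Part 1 escalation and say nothing about C or E.

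**2. When the combination starts in C and E.** Cycles last 14 days, so Cycle 3 Day 1 = 1 + 2 × 14 = Day 29. Protocol Table 12 allows ±3 days. If visits are anchored to the nominal day, the start falls on Days 26 to 32. If each cycle may run 11 to 17 days, it falls on 1 + 22 = Day 23 to 1 + 34 = Day 35. Even if Days 1 to 28 were applied to C and E, combination exposure inside that period would nominally be nil and at most 3 days (Days 26–28) or 6 days (Days 23–28).

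**3. What the DLT cell would mean.** The period is assigned to A, B and D. The SAP counts a form field with no day or group limit and does not say how C and E are to be shown. The C and E rate is therefore undefined: not assessed, rather than calculated.

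**4. What an unassessed zero could conceal (illustration).** Assume a full cohort of 6, all reaching the combination, and a true rate p of DLT-type events over 28 combination days. The rates are assumptions; the documents give none.

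P(at least one event in 6) = 1 − (1−p)⁶
- p = 10%: 46.9%
- p = 20%: 73.8%
- p = 33.3%: 91.2%

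Even a properly assessed 0/6 would have an exact upper 95% bound of 1 − 0.05^(1/6) = 39.3% one-sided, or 1 − 0.025^(1/6) = 45.9% two-sided.

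**5. Which TEAE tables are affected.**
- On the Phase 1 FAS (at least one dose of any study drug): overall summary 3.2.1.1, Grade 3 or higher 3.2.6.1, INCAGN01949-related 3.2.7.1 and 3.2.10.1. For C and E these pool 2 × 14 = 28 days of monotherapy with later exposure. In a cohort of 6, each run-in dropout is 1/6 = 17% of the denominator and has no combination exposure.
- On the partner-drug sets of SAP 5.3.1: nivolumab-related 3.2.8.1, 3.2.11.1 and 3.2.14.1; ipilimumab-related 3.2.9.1, 3.2.12.1 and 3.2.15.1. Run-in dropouts are already excluded here.

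**The case against.** The best defense is that confining DLTs to Part 1 looks deliberate, and that Part 2 is monitored by other means. C and E open only at doses already tolerated in A or D and are capped at that group's MTD. Enrollment pauses if more than 40% of a treatment group have Grade 3 or 4 INCAGN01949-related AEs, and that rule has no time limit (Protocol 4.1.2). A lower MTD may follow from later toxicity (Protocol 5.4.2). The primary safety endpoint is AE frequency, duration and severity, and causality is recorded per agent. All of this stands, and it limits the point to reporting.

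It does not supply a DLT rate for C and E. The pause rule counts only INCAGN01949-related events, run-in time included. With 6 subjects in a group it needs 3 (2/6 = 33%), and it would trip with probability 9.9% or 25.6% at a true rate of 20% or 30%. The provision allowing AEs at any time to count toward DLTs sits in the Phase 2 text (Protocol 4.1.3 and Table 8), so it does not clearly reach Part 2 of Phase 1.

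It is also fair that no comparison of C with A or E with D is planned. Protocol 4.2 limits comparisons to pretreatment conditions, 9.3 plans no formal tests, and 1.5.3 argues for priming from antitumor activity, not tolerability. The risk is an informal reading of adjacent columns.

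A reader might further infer that C and E lack a replacement rule, because the first rule in Protocol 4.3.2 covers "any subject who withdraws from treatment before the completion of the DLT observation period for any reason other than a DLT". Another item in that list is redacted, so this cannot be judged.

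**Conclusion.** The point holds as a reporting gap. C and E have no DLT evaluation period, yet the SAP plans a DLT percentage for them. Their all-cause and INCAGN01949-related TEAE tables do not isolate combination exposure.

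Two stronger readings are tempting and are not supported:
- *The DLT rate in C and E is zero by construction.* The SAP's form-field rule has no day or group limit, so a site could flag an event. If Days 1 to 28 were applied, run-in monotherapy DLTs could also count. Zero is likely, not forced.
- *The Phase 1 primary objective goes unanswered.* It promises no DLT rate per schedule. Groups A, B and D supply combination DLTs, and AEs are still collected in C and E. Only the DLT component and the combination-period safety description for the run-in schedule are missing.

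The 47%, 74% and 91% figures rest on assumed rates and a full cohort of 6. Protocol 4.1.2 says up to 6 per dose, and the split of the 52 subjects across groups is not given, so the practical weight depends on how many entered C and E. Phase 2 will not open, so the effect is confined to the Phase 1 report.

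**What to change.** Reporting changes only; no dosing or clinical rule is touched.

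1. In SAP 8.2.2 and 8.2.4, Table 3.2.1.1 and the DMC outputs, show DLTs for C and E as *not assessed*, with a footnote citing Protocol 5.4.2.
2. For C and E, split the overall, Grade 3 or higher and INCAGN01949-related TEAE tables at the first nivolumab dose. Report the run-in period on all dosed subjects and the combination period on the nivolumab FAS of SAP 5.3.1. Assign events by onset date. Protocol 8.1.2 already records each change in severity as a separate event with its own start date, so worsening after the first nivolumab dose can be placed in the combination period.
3. Optionally, list events in C and E after Cycle 3 Day 1 that match the Table 8 event types, labelled retrospective and descriptive. The Table 8 item on receiving the planned doses within the 28-day period has no counterpart in C or E, and the listing should say so.

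The cost is SAP wording and a few more table columns with small denominators, from data already collected. Item 3 would also need a one-off medical review. No new subjects or visits are required.
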